9.4.2.2 Secondary Efficacy Analyses

Analyses of change from baseline and observed and change from baseline for diurnal IOP will be performed in a manner similar to the primary efficacy analysis.

9.4.3 Safety Analyses

Safety analyses will be performed on all subjects in the Safety Analysis Set. The assessment of safety will be based on the summary of ocular and non-ocular treatment emergent adverse events (TEAEs), BCVA, central corneal thickness, vital signs, clinical laboratory tests, and ophthalmic exams using slit-

lamp biomicroscopy and dilated ophthalmoscopy. Summaries will be provided by treatment group, and for ocular assessments separately by study-eye and non-study-eye.

9.4.3.1 Adverse Events

AEs will be coded using MedDRA (most current version) and categorized by system organ class using preferred terms. Separate summaries of AEs related to treatment (as reported by the Investigator) and by severity will be presented. The number of deaths and SAEs will also be presented, and events leading to discontinuation from the study will be listed and tabulated.

9.4.3.2 Clinical Laboratory Tests

Summary statistics for observed and change from baseline for serum chemistry and hematology laboratory tests will be presented.

9.4.3.3 Other Safety Evaluations

Summary statistics for observed and change from baseline for BCVA, central corneal thickness, and vital signs will be presented. Abnormalities in slit-lamp biomicroscopy and dilated ophthalmoscopy will be summarized by frequency and percentage.

9.5 Interim Analysis

Not applicable.

9.6 Subgroup Analyses

Subgroup analyses will be described in the SAP.

9.7 Exploratory Analyses

Not applicable.

9.8 Missing or Unused Data

Missing data for IOP will be imputed using LOCF methodology as a sensitivity analysis for the primary endpoint and diurnal IOP. Otherwise, observed data will be analyzed at each visit and analyzed using MMRM which assumes MAR.

9.9 Tabulation of Individual Subject Data

All data collected in this study will be presented in individual subject data listings for all subjects.

10 Supporting Documentation and Operational Considerations

10.1 Regulatory Issues, Ethical Concerns, and Study Oversight

10.1.1 Informed Consent Process

10.1.1.1 Consent/Accent Documents

Consent forms describing in detail the study intervention, study procedures, and risks are given to the subject and written documentation of informed consent is required prior to starting intervention/administering study intervention.

10.1.1.2 Consent Procedures and Documentation

Informed consent is a process that is initiated prior to the individual's agreeing to participate in the study and continues throughout the individual's study participation. Consent forms will be Investigational Review Board (IRB)-approved and the subject will be asked to read and review the document. The Investigator will explain the research study to the subject and answer any questions that may arise. A verbal explanation will be provided in terms suited to the subject's comprehension of the purposes, procedures, and potential risks of the study and of their rights as research subjects. Subjects will have the opportunity to carefully review the written consent form and ask questions prior to signing. The subjects should have the opportunity to discuss the study with their family or surrogates or think about it prior to agreeing to participate. The subject will sign the informed consent document prior to any procedures being done specifically for the study. Subjects must be informed that participation is voluntary and that they may withdraw from the study at any time, without prejudice. A copy of the informed consent document will be given to the subjects for their records. The informed consent process will be conducted and documented in the source document (including the date), and the form signed, before the subject undergoes any study-specific procedures. The rights and welfare of the subjects will be protected by emphasizing to them that the quality of their medical care will not be adversely affected if they decline to participate in this study.

10.1.2 Study Discontinuation and Closure

This study may be temporarily suspended or prematurely terminated if there is sufficient reasonable cause. Written notification, documenting the reason for study suspension or termination, will be provided by the Sponsor to the Investigators and regulatory authorities. If the study is prematurely terminated or suspended, the Principal Investigator (PI) will promptly inform study subjects and the reviewing IRB. Study subjects will be contacted, as applicable, and be informed of changes to study visit schedule.

Circumstances that may warrant termination or suspension may include, but are not limited to:

- Determination of unexpected, significant, or unacceptable risk to subjects
- Demonstration of efficacy that would warrant stopping
- Insufficient compliance to protocol requirements
- Data that are not sufficiently complete and/or evaluable
- Determination that the primary endpoint has been met
- Determination of futility

Study may resume once concerns about safety, protocol compliance, and data quality are addressed, and satisfy the Sponsor, IRB and/or FDA.

10.1.3 Confidentiality and Privacy

Subject confidentiality and privacy will be strictly held in trust by the participating Investigators, their staff, and the Sponsor(s) and their interventions. This confidentiality will be extended to cover testing of biological samples and genetic tests in addition to the clinical information relating to subjects. Therefore, the study protocol, documentation, data, and all other information generated will be held in strict confidence. No information concerning the study or the data will be released to any unauthorized third party without prior written approval of the Sponsor.

All research activities will be conducted in as private a setting as possible.

The Study Monitor, other authorized representatives of the Sponsor, representatives of the IRB, regulatory agencies or pharmaceutical company supplying study product will be able to inspect all documents and records required to be maintained by the Investigator, including but not limited to, medical records (i.e., office, clinic, or hospital) and pharmacy records for the subjects in this study. The clinical study site will permit access to such records.

The study subject's contact information will be securely stored at each clinical site for internal use during the study. At the end of the study, all records will continue to be kept in a secure location for as long a period as dictated by the reviewing IRB, Institutional policies, or Sponsor requirements.

Study subject research data, which is for purposes of statistical analysis and scientific reporting, will be transmitted to and stored at Lexitas Pharma Services, Inc. This will not include the subject's contact or identifying information. Rather, individual subjects and their research data will be identified by a unique study identification number. The study data entry and study management systems used by clinical sites and by Lexitas research staff will be secured and password protected. At the end of the study, all study databases will be de-identified and archived at Lexitas.

10.1.4 Key Roles and Study Governance

The Manual of Procedures (MOP) will include a list of study team roles and responsibilities of those involved in the conduct, management, or oversight of the trial.

10.1.5 Clinical Monitoring

Lexitas Pharma Services, Inc. will conduct the clinical monitoring for this study. A clinical Monitoring Plan is to be used, which will describe in detail who will conduct the monitoring, at what frequency monitoring will be done, at what level of detail monitoring will be performed and the distribution of monitoring reports.

10.1.6 Quality Assurance and Quality Control

Quality control (QC) procedures will be implemented beginning with the data entry system and data QC checks that will be run on the database will be generated. Any missing data or data anomalies will be communicated to the site(s) for clarification/resolution.

Following written Standard Operating Procedures (SOPs), the monitors will verify that the clinical trial is conducted and data are generated and biological specimens are collected, documented (recorded), and reported in compliance with the protocol, International Council for Harmonisation (ICH) Good Clinical Practice (GCP), and applicable regulatory requirements (e.g., Good Laboratory Practice [GLP], Good Manufacturing Practices [GMP]).

The investigational site will provide direct access to all trial related sites, source data/documents, and reports for the purpose of monitoring and auditing by the Sponsor, and inspection by local and regulatory authorities.

10.1.7 Data Handling and Record Keeping

10.1.7.1 Data Collection and Management Responsibilities

Data collection is the responsibility of the clinical trial staff at the site under the supervision of the site's Investigator. The Investigator is responsible for ensuring the accuracy, completeness, legibility, and timeliness of the data reported.

All source documents should be completed in a neat, legible manner to insure accurate interpretation of data. Data recorded in the eCRF derived from source documents should be consistent with the data recorded on the source documents.

Clinical data (including AEs, concomitant medications, and expected adverse reactions data) will be entered into IBM Clinical Development, a 21 CFR Part 11-compliant data capture system provided by Lexitas Pharma Services, Inc. The data system includes password protection and

internal quality checks, such as automatic range checks, to identify data that appear inconsistent, incomplete, or inaccurate. Clinical data will be entered directly from the source documents.

10.1.7.2 Study Records Retention

Study documents should be retained for a minimum of 2 years after the last approval of a marketing application in an ICH region and until there are no pending or contemplated marketing applications in an ICH region or until at least 2 years have elapsed since the formal discontinuation of clinical development of the study intervention. These documents should be retained for a longer period, however, if required by local regulations. No records will be destroyed without the written consent of the Sponsor, if applicable. It is the responsibility of the Sponsor to inform the Investigator when these documents no longer need to be retained.

10.1.8 Protocol Deviations

A protocol deviation is any noncompliance with the clinical trial protocol, ICH GCP, or Manual of Procedures (MOP) requirements. The noncompliance may be either on the part of the subject, the Investigator, or the study site staff. As a result of deviations, corrective actions are to be developed by the site and implemented promptly.

These practices are consistent with ICH GCP:

- 4.5 Compliance with Protocol, sections 4.5.1, 4.5.2, and 4.5.3
- 5.1 Quality Assurance and Quality Control, section 5.1.1
- 5.20 Noncompliance, sections 5.20.1, and 5.20.2.

It is the responsibility of the site's Investigator to use continuous vigilance to identify and report deviations. All deviations must be addressed in study source documents, reported to the reviewing IRB (as applicable per the IRB policies), the Contract Research Organization and/or Sponsor. The site Investigator is responsible for knowing and adhering to the reviewing IRB requirements. Further details about the handling of protocol deviations will be included in the MOP.

12.1 Appendix 1: Schedule of Procedures and Assessments

Study Period	Screening	Washout ¹	Baseline	Treatment Period				End of Treatment
				2	3	4	5	
Visit No.	1		2					6
Visit Window	Day-35 to -1		Day 0	Day 1	Day 7 (+2)	Day 14 (+2)	Day 21 (+2)	
Informed consent ²	X							
Ocular and medical history	X		X					
Demographics	X							
Inclusion/Exclusion criteria	X		X					
BCVA	X		X	X	X	X	X	
Biomicroscopy ³	X		X	X	X	X	X	
IOP	X			X ⁴				
Diurnal IOP ⁵			X		X	X	X	
Cup-to-disc ratio	X							X
Dilated ophthalmoscopy	X							X ⁶
Pachymetry ⁷	X							X
Gonioscopy ⁸	X							

¹ Washout period: Prostaglandins, β-adrenoceptor antagonists, kinase inhibitors (4 weeks), adrenergic agonists (2 weeks), muscarinic agonists and carbonic anhydrase inhibitors (5 days)

² Informed consent will be obtained prior to the conduct of any study specified or associated procedures or evaluations.

³ Biomicroscopy of anterior segment includes corneal epithelium, bulbar and lower conjunctiva, and lens.

⁴ Measured at 8:00AM

⁵ Measured at 8:00AM, 10:00AM and 4:00PM

⁶ After the last IOP measurement

⁷ Central corneal thickness will be measured at entry for IOP interpretation. Pachymetry performed within 3 months of screening is acceptable. Ultrasound and optical pachymetry is permissible provided that the same methodology is used at Visits 1 and 6.

⁸ Gonioscopy performed within 3 months of Visit 1 is acceptable.

Study Period	Screening	Washout ¹	Baseline	Treatment Period			End of Treatment
Visit No.	1		2	3	4	5	6
Visit Window	Day-35 to -1		Day 0	Day 1	Day 7 (+2)	Day 14 (+2)	Day 21 (+2)
Visual field ⁹	X						
Optical Coherence Tomography	X ¹⁰						
Blood chemistry, hematology	X						X
BP, HR	X		X	X	X	X	X
Pregnancy test ¹¹	X		X				X
Randomization			X				
Study drug administration in clinic				X ¹²	X ¹³		X ¹³
Dispense investigational product				X	X	X	
Collect study drug					X	X	X
Prior/Concomitant medications	X		X	X	X	X	X
Adverse event assessment			X	X	X	X	X

Abbreviation key: BCVA=best corrected visual acuity; BP=blood pressure; HR=heart rate; IOP=intraocular pressure

⁹ Visual field within 3 months of Visit 1 is acceptable, provided that it is reliable and meets the requirement for automated threshold visual field (e.g., 30-2 or 24-2 Humphrey). Unreliable entry fields must be repeated prior to study drug dispensation.

¹⁰ Optical Coherence Tomography within 3 months of Visit 1 is acceptable.

¹¹ Women of childbearing potential only

¹² After 8:00AM IOP measurement

¹³ After 8:00AM and prior to 10:00AM IOP measurement

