Investigational product(s):	VVN539 ophthalmic solution 0.02% (3mL in 5 mL bottles) VVN539 ophthalmic solution 0.04% (3mL in 5 mL bottles) VVN539 ophthalmic solution vehicle (3mL in 5 mL bottles)

Dosing regimen:	Both eyes (OU), q.d. (morning) for 7 days, then q.d. (evening) for 7 days, and then b.i.d. for 7 days.
Assessments/Evaluations:	
Efficacy:
 
• IOP for efficacy will be measured by Goldmann applanation tonometry at 8:00AM, 10:00AM and 4:00PM at Visits 2, 4, 5 and 6. 
Safety:
 
• Adverse event monitoring• Best Corrected Visual Acuity (ETDRS)• IOP• Biomicroscopy of anterior segment• Central corneal thickness• Cup-disc ratio• Ophthalmoscopy (dilated)• Heart rate and blood pressure (BP)• Blood chemistry, hematology
Duration of study:	There are a total of 6 clinical visits over 8 weeks (up to 5 weeks of washout and 3 weeks of study treatment)

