3.1 Overall Design of the Study

This is a prospective, parallel-comparison, multi-center, double-masked, randomized, vehicle-controlled dose-response study assessing the safety and ocular hypotensive efficacy of VVN539 in subjects with POAG or OHT. Approximately 60 subjects will be randomized into one of two active treatment arms or a control arm (20 subjects per cohort):

- Arm 1: 0.02% VVN539 ophthalmic solution
- Arm 2: 0.04% VVN539 ophthalmic solution
- Arm 3: VVN539 ophthalmic solution vehicle

Treatment assignments will be masked to VivaVision, study subjects, Investigators, and site staff.

The study involves 6 clinic visits, including screening, baseline, and treatment visits. The study is open to subjects with OHT and POAG who are either treatment-naïve or are already on ocular hypotensive medication. Subjects on ocular hypotensive who meet screening inclusion and do not meet screening exclusion criteria at Visit 1 will discontinue their prior ocular hypotensive medication for up to 35 days before returning to the site for Visit 2 (baseline). Treatment naïve subjects can return for the baseline visit as early as the day after Visit 1. Subjects meeting all baseline inclusion criteria and none of the baseline exclusion criteria will be randomized into one of the study arms and will return to the study site the next day for the first treatment. Three different dosing regimens (once a day [q.d.] in the morning, q.d. in the evening and twice a day [b.i.d.]) will be tested for 7-9 days, each.

Figure 1: Study Treatment

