12.7 Appendix 7: Pachymetry

Corneal thickness evaluation (in microns) will be performed using a calibrated ultrasonic or optical pachymeter, provided that the same method is used for all measurements. Measurements will be taken in the central cornea after instilling topical anesthetic. A total of three readings will be obtained for each eye. Care should be taken to place the probe perpendicular to the corneal surface and to not compress the cornea.

Pachymetry is performed at Visit 1 and Visit 6.

- At Visit 1, pachymetry within 3 months of the visit is acceptable.
- At Visit 6, Pachymetry is to be performed after the last IOP measurement.

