9.5.1.4.4. Central Corneal Thickness

Corneal thickness evaluation (in microns) will be performed using a calibrated ultrasonic or optical pachymeter, provided that the same method is used for all measurements. Measurements will be taken in the central cornea after instilling topical anesthetic. A total of three readings will be obtained for each eye. Care should be taken to place the probe perpendicular to the corneal surface and to not compress the cornea.

Pachymetry is performed at Visit 1 and Visit 6.

- At Visit 1, pachymetry within 3 months of the visit is acceptable.
- At Visit 6, Pachymetry is to be performed after the last IOP measurement.

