9.7.1.3. Analysis of Demographic and Baseline Characteristics

9.7.1.3.1. Demographics and Disease Characteristics

Demographic and baseline disease characteristics including age (years), age group (18-<45, \geq 45), sex, race, ethnicity, iris color, study eye (OD/OS), normality of nerve fiber layer thickness, baseline diurnal IOP of the study eye, and baseline IOP at 8:00 AM, 10:00 AM, and 4:00 PM will be summarized descriptively by treatment group and overall using the FAS, Per Protocol, and Safety Analysis Sets. For categorical parameters, the percentages will be calculated overall and based on the number of subjects in each treatment group based on non-missing observations.

Ocular baseline characteristics for central corneal thickness (average of three measurements), gonioscopy, and visual field will be summarized by study eye and non-study eye.

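### A pachymetry up to 3 months old may serve as the Visit 1 value and so become the baseline for corneal-thickness change, with no express requirement for three readings or for the Visit 6 device

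*Protocol*

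**What the plan says.** **The allowance.** Protocol Appendix 1, footnote 7: "Pachymetry performed within 3 months of screening is acceptable". The SAP's schedule (Appendix I, Table 1, footnote 7) repeats it. SAP 9.5.1.4.4 says "At Visit 1, pachymetry within 3 months of the visit is acceptable", and Protocol Appendix 7 has the same rule. The Visit 1 procedure list (Protocol 7.1.1) gives a 3-month allowance for visual field, OCT and gonioscopy but lists pachymetry without one.

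**The measurement standard.** Appendix 7 asks for a calibrated ultrasonic or optical pachymeter, one method for all measurements, and "A total of three readings will be obtained for each eye". Footnote 7 requires the method, ultrasound or optical, to match between Visits 1 and 6. SAP 9.7.1.3.1 treats baseline CCT as the mean of three readings.

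**The use of the value.** Appendix 7: "Pachymetry is performed at Visit 1 and Visit 6". CCT is listed as a safety assessment in Protocol 2.2.3 and SAP 9.5.1.4. Protocol 9.4.3.3: "Summary statistics for observed and change from baseline for BCVA, central corneal thickness, and vital signs will be presented". The SAP's general baseline rule (9.7.1) takes the last measurement through Visit 2. It sets no age limit and makes no exception for CCT.

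**The concern.** Visual field, OCT and gonioscopy may also be historical, but none is scheduled after Visit 1, so no change score depends on them. Pachymetry is repeated at Visit 6. Footnote 7 gives the purpose of the entry reading as interpreting IOP, yet the plan then uses the same reading as a safety baseline.

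For a subject with a historical value, the CCT change spans the months before screening and any washout as well as about 3 weeks of treatment. It may also start from a reading made to a different standard. This is a first-in-human trial with about 20 subjects per arm and one scheduled post-dose pachymetry, so a weak baseline cannot be repaired later.

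**Working it through.** **1. Timeline.** The plan's own duration reproduces: 35 days of screening and washout + 21 days of treatment = 56 days = 8 weeks.

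Inputs: historical reading up to 3 months before Visit 1 (taken as 91 days; 89 to 92 by calendar), Visit 1 as early as Day -35, first dose on Day 1, Visit 6 on Day 21 (+2).

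| Baseline reading | Longest gap to Visit 6 (Day 23) |
|---|---|
| Historical, Visit 1 on Day -35 | 91 + 35 + 23 = 149 days (147 to 150), about 4.9 months |
| Historical, Visit 1 on Day -1 | 91 + 1 + 23 = 115 days, about 3.8 months |
| Measured at Visit 1 on Day -35 | 35 + 23 = 58 days |

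Counted to first dose, the oldest historical reading is 91 + 35 + 1 = 127 days old, about 4.2 months. Protocol 3.1 says each regimen "will be tested for 7-9 days, each". If those windows accumulate, Visit 6 could fall on Day 27, which adds 4 days to each gap in the table.

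**2. Measurement error of the change.** Let s be the SD of one reading, with independent errors. Visit 6 is a mean of three readings, so its error variance is s²/3. If the baseline is a mean of k readings on the same device:

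- Var(change) = s²/k + s²/3
- Ratio to the three-reading case = (1/k + 1/3) / (2/3)

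| Readings at baseline (k) | Var(change) | Variance ratio | SD ratio |
|---|---|---|---|
| 3 | 2s²/3 | 1.00 | 1.00 |
| 2 | 5s²/6 | 1.25 | 1.12 |
| 1 | 4s²/3 | 2.00 | 1.41 |

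The ratios do not depend on s. To show scale only, with s assumed to be 5 to 8 µm (not in the documents), the SD of change from measurement error is 4.1 to 6.5 µm for k = 3 and 5.8 to 9.2 µm for k = 1.

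**3. Share of subjects affected.** The documents do not say how many subjects would use a historical value. If a proportion p has a single-reading baseline, the average error variance is (2s²/3)(1 + p). The measurement-error part of an interval for mean change then widens by √(1 + p) - 1: 0% at p = 0, 22% at p = 0.5, 41% at p = 1.

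**4. Device.** A device difference with SD d would add d² to Var(change). The documents give no value for d, so no result here relies on one.

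**The case against.** **The historical reading may already have to meet Appendix 7.** The 3-month allowance sits in the section that sets three readings and one method, so a historical value could be read as accepted only on those terms. That is a fair reading, and under it measurement error is not inflated. But it is not stated. A clinic reading predates the study procedures, and footnote 7 repeats only the matching of method. The visual-field allowance, by contrast, carries an explicit reliability condition (footnote 9). The ambiguity stands.

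**Age alone is not shown to do harm.** A reader might infer that a five-month-old baseline is wrong because of its age. The documents do not support that: nothing in them shows CCT drifting over 149 days rather than 58, and the variance formula has no term for elapsed time. The 149 days is also a worst case.

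**Large magnitudes would rest on assumption.** With s = 8 µm and an assumed d = 15 µm, the variance for a single historical reading is 4(64)/3 + 225 = 310 µm², of which 225 (73%) is the assumed device term. Nor does the current text require one physical device for two in-study readings, so this weakness is not confined to historical values.

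**No arm comparison of CCT is planned.** SAP 9.7.1.6 excludes statistical comparisons between groups for safety unless specified, and none is specified for CCT. Slit-lamp examination with graded corneal edema, and visual acuity, are done at every visit and give fresher corneal monitoring. Both points stand and limit what is at stake.

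**Conclusion.** The point holds as a modest weakness in a descriptive safety summary. A reading taken outside study procedures can become the CCT safety baseline, at most about 149 days before Visit 6 against 58 if measured at Visit 1. The measurement cost runs from nothing (three readings, same device) to a doubled error variance and an SD about 41% larger (single reading). The ratios assume independent reading errors of equal SD. They cover measurement error only; true variation between subjects in CCT change would make the relative widening smaller.

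Two stronger readings should be set aside. The historical reading is not off-protocol, because the protocol expressly allows it. Nor is there a case for bias between arms: the readings predate randomization, so older values are balanced in expectation. The result is added noise and individual changes that are harder to interpret. The primary IOP endpoint is unaffected.

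**What to change.** In Protocol Appendix 1 footnote 7, Protocol Appendix 7, SAP 9.5.1.4.4 and footnote 7 of the SAP schedule, allow a historical pachymetry only as a pre-check of inclusion criterion 5. Require the three-reading pachymetry at Visit 1 in every subject, on the same instrument as Visit 6, and name its mean as the baseline for CCT change. This also brings those sections into line with the Visit 1 list in Protocol 7.1.1.

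The same edit can close a related gap. SAP 9.7.1.6 names CCT as a safety variable, but subsections 9.7.1.6.1 to 9.7.1.6.6 contain no CCT analysis, so the change summary promised in Protocol 9.4.3.3 is not specified there.

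The cost is a wording change in both documents and, for subjects who already have a recent value, a few minutes of a procedure already scheduled at Visit 1. No extra visit is needed.
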